## **STUDY INTERVENTIONS**

### **Interventions**

Providers employ uniform feeding and nutritional practices in our NICU infants as per our standardized guidelines, which applies to nutrient and volume modifications. However, upon randomization and allocation, individual protocols are complied with. Upon completion of screening, enrollment and randomization, the assigned feeding management strategy was relayed to parents and the medical team. Subjects in both arms received omeprazole off label, as a therapeutic choice (27, 28) at a recommended dose of 0.75 mg/kg/dose BID (15, 27, 29). The conventional approach was to not adjust provider recommended feeding strategies (i.e. fed in any

position, duration, volume, and postprandial position). The study approach utilized a modified feeding strategy including: a) feeding in the right lateral position to facilitate intra-prandial gastric emptying (30), b) feeding duration of at least 30 min utilizing pacing when orally fed to ensure completion of prescribed volumes or via pump to ensure steady delivery of milk if gavage-fed (21), c) supine postprandial position (31), and d) limiting total feeding volume to  $\leq 140$  ml/kg/day (21).

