### **Compliance measures, side effects and adverse events**

Compliance to randomization, allocation and interventions, and drop outs are reported (**Fig 1, Table 2**). Total fluid volume was identical at inception but both groups showed a reduction compared to baseline at time-2. However, as per the trial design, the study group showed significantly (all  $p < 0.05$ ) lower volume intake, feeding in right side lying position, and postprandial supine position. Feeding duration of actual feeding was increased in the study group but not statistically different from the conventional group. No side effects or adverse events were reported in either group.

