is justifiable in future trials, as nearly 40% of infants are in this severe range, and it is possible to study such a group in larger clinical trials based on pH and impedance criteria, while employing placebo for equipoise. Since time-limited PPI therapy concurrent with feeding strategies was neither shown to be beneficial or associated with adverse effects, we believe that, it is safe to include a completely untreated placebo group in future trials that enroll patients with objectively determined acid-GERD. 2) The management strategies were tightly regulated, as were feeding and testing guidelines, and the treatment was uniformly delivered across the two groups. The patient population was homogeneous and constituted a fair representation from the convalescing NICU population. In addition, the randomized controlled allocation accounted for premature or full-term birth, and the indeterminate or determinate acid-GERD per ARI. Furthermore, the prevalence of oxygen requirement or tube feeding at discharge was not different between groups. 3) Our study trial has many elements of objectivity. Determination of I-GERQ-R and ARI, as well as monitoring feeding methods during the trial are strengths. Thirty-six percent of those with aerodigestive and or cardiorespiratory symptoms perceived by their clinicians to be due to GERD prior to trial consent, were not randomized and were also never treated with a PPI as the esophageal acid exposure was normal (ARI < 3%). In a purely symptom-based clinical trial, all those 688 infants screened would have likely been treated for presumed GERD. In the current study, only those that had true ARI exposure have been randomized and treated. Therefore, the symptom-based approach alone is not the solution to diagnose and treat GERD. Interestingly, perception of symptoms (IGERQR scores) decreased across time regardless of treatment group allocations (**Fig 2**). These findings strongly support maturational effect. As both groups were treated with PPI, placebo-included RCTs are needed to determine if maturation alone will improve objectively determined acid- and non-acid-GERD. 4) Absence of pH-impedance testing to confirm true acid-GERD prior

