**Table 3. Feeding and I-GERQ-R Outcomes by Feeding Method at Inception**

Outcome	Conventional	Study	P-value
Among those Tube fed at Inception			
Achieved exclusive oral feeding	N = 18	N = 20	
Achieved I-GERQ-R decrease $\geq 6$	11 (61)	7 (35)	0.11
Achieved PO or I-GERQ-R decrease $\geq 6$	7/17 (41)	8 (40)	0.94
Achieved exclusive oral feeding + I-GERQ-R decrease $\geq 6$	14 (78)	13 (65)	0.39
	4/17 (24)	2 (10)	0.38
Among those PO fed at Inception	N = 17	N = 17	
Maintained PO	16 (94)	17 (100)	1.0
Achieved I-GERQ-R decrease $\geq 6$	4/14 (29)	5/14 (36)	1.0
Maintained PO or I-GERQ-R decrease $\geq 6$	16 (94)	17 (100)	1.0
Maintained PO + I-GERQ-R decrease $\geq 6$	4/14 (29)	5/14 (36)	1.0

[figure not shown]
Data presented as n (%).

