## **6.0 Procedures Involved\***

### **6.1 Study design:**

- Study design and setting: This is a Single Center Prospective Randomized, Blinded Controlled Trial. Consented subjects will undergo 1:1 randomization into either innovative feeding strategy and standard therapy arms.
- Patient Population: Potential study subjects are those that are referred by their attending physician for evaluation and management of potential GERD, the key symptoms being irritability and arching, gagging, choking, coughing, aspiration, life threatening events, swallowing problems, and/or failure to thrive. I-GERQ-R questionnaire will be completed as per guidelines. Each patient must have a signed consent from parent/legal guardian prior to initiation of screening for the trial.
- Inclusion Criteria: Hospitalized convalescing infants with aerodigestive symptoms or admitted for GERD symptoms, < 42 weeks GA. Infants will be included if PMA at time of study is  $\geq$  34 wks age and  $\leq$  60 wks. Subjects must be on full enteral feeds defined as  $\geq$  150mL/k/day. Infants must be breathing unaided, and nasal cannula oxygen up to 1 LPM is allowed. In subjects receiving empiric prokinetics or acid suppressive agents, the medications need to be stopped for  $\geq$  72 hr prior to evaluation.
- Exclusion Criteria: Infants with known genetic, metabolic or syndromic disease, neurological diseases such as Grade III or IV intra ventricular hemorrhage or perinatal asphyxia, GI malformations and surgical GI conditions.
- Tests and procedures
  - Twenty-four-hour pH and impedance ordered diagnostically for suspected GERD
  - If RI  $>3$  and infant meets all above criteria, infant randomized into conventional or study group
  - Esophageal manometry performed
  - 4 weeks of the study intervention for the study group and standard treatment for the conventional group while collecting data on symptoms, feeding position, duration and volume

- Omeprazole stopped after 4-week course.
- Repeat esophageal manometry and pH impedance testing done after 1 week off omeprazole (at week 5). If the providers/parents are resistant or refuse to stop the medication, repeat testing will still be done, and the alteration will be noted.

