## **14.0 Risks to Subjects\***

This study includes the risk associated with the nasal placement of the manometry probe and pH/impedance catheter. These risks are similar to the risks associated with the placement of a nasogastric feeding tube in infants which is frequently done for tube feeding infants both in the hospital and sometimes at home

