## **17.0 Provisions to Monitor the Data to Ensure the Safety of Subjects\***

- Subjects are monitored throughout study procedures by a trained Registered nurse
- Meetings of the Data Safety Monitoring Board will take place on a quarterly basis.
- The study is overseen by the IRB at NCH and annual reports will be submitted
- A Data safety monitoring plan will be implemented with reports given to the DSMB and the IRB and NIDDK when appropriate.
- Subjects who remain hospitalized throughout the study period will be monitored by lab staff via review of their electronic medical record and review of bedside documentation
- Subjects who have been discharged to home will be monitored by weekly telephone communication with parents and caregivers
- Parents will be told whom to contact in case of concerns

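### The Discussion infers that an untreated placebo group is safe from a trial in which both randomised arms received omeprazole

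*Combined protocol and SAP*

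**What the plan says.** Item 1 of the trial strengths in the report's Discussion gives two premises: "Since time-limited PPI therapy concurrent with feeding strategies was neither shown to be beneficial or associated with adverse effects". From these it concludes, for future trials in infants with objectively determined acid reflux disease: "we believe that, it is safe to include a completely untreated placebo group in future trials".

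On exposure, the report's Interventions section states: "Subjects in both arms received omeprazole off label, as a therapeutic choice". Protocol sections 6.1 and 8.0 plan 4 weeks of omeprazole followed by a week off it before repeat testing. Section 6.1 then adds: "If the providers/parents are resistant or refuse to stop the medication, repeat testing will still be done". Revision 3 in the IRB revision history (December 2013) records that parents and providers would not permit stopping at 4 weeks, and lets infants stay on the drug at the follow-up evaluation.

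On harms, the report's section on compliance, side effects and adverse events says: "No side effects or adverse events were reported in either group". It gives no denominator, observation window or method of ascertainment.

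**The concern.** The sentence moves from infants who were on a drug to infants who would be off it. Not seeing harm during treatment bears on the safety of the treatment. It does not bear on what happens when treatment is withheld, and that is the question a placebo arm raises.

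The other premise, that the drug was not shown to be beneficial, has the same gap. The randomised contrast was the feeding bundle, so the trial could not have shown benefit or lack of benefit from omeprazole.

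At stake is a safety statement about leaving infants with measured acid reflux untreated, which a later protocol or ethics submission could cite as a finding of this trial.

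**Working it through.** **Step 1. Who was observed without acid suppression?**

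| Group | Acid suppression | Bears on the conclusion? |
|---|---|---|
| Conventional arm, n = 36 | Omeprazole | No |
| Study arm, n = 40 | Omeprazole | No |
| Screened, index below 3%, n = 246 | Never treated, per the Discussion | No: not randomised, and outside the acid-reflux population named in the sentence |
| Planned week off omeprazole (protocol 6.1, 8.0) | Off drug after 4 weeks on it | No: not a randomised comparison, not compulsory, and no safety results reported for it |

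Randomised infants assigned to no acid suppression: 0. The Discussion itself says that placebo trials are needed because both groups were treated.

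**Step 2. Was exposure time-limited?** Sections 6.1 and 8.0 set 4 weeks. Revision 3 and the exception in section 6.1 allow longer. The number of infants who continued appears nowhere, so the premise can be neither confirmed nor sized.

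**Step 3. What does the zero exclude?** The report's figure is zero events. A count of zero cannot be re-derived, but its precision can be calculated. The one-sided 95% upper limit p solves (1 − p)^n = 0.05, so p = 1 − 0.05^(1/n). With n from Table 1:

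- conventional, 0/36: 1 − 0.05^(1/36) = 0.0798, or 8.0%
- study, 0/40: 1 − 0.05^(1/40) = 0.0722, or 7.2%
- both arms, 0/76: 1 − 0.05^(1/76) = 0.0387, or 3.9%
- untreated, n = 0: (1 − p)^0 = 1 for every p, so no rate is excluded

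The first three limits hold only if every event would have been captured in every infant, and all three concern infants assigned omeprazole.

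The chance of seeing no event in 76 infants, (1 − p)^76, is 0.466 at a true rate of 1%, 0.215 at 2%, 0.099 at 3% and 0.020 at 5%.

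**Step 4. Why the window matters.** Table 2 gives a median of 25 days [11–45] from inception to discharge among the 72 infants analysed. At least half had therefore gone home before day 28, after which section 17.0 relies on weekly telephone contact. The report does not say which period the zero covers.

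**The case against.** The sentence is hedged as a belief. It is one line of the Discussion, and neither the Abstract's conclusions nor the Conclusion section repeats it. The report elsewhere says that whether the drug is needed remains to be tested. All of that stands. It lowers the prominence of the claim but supplies no data for it.

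A reader might infer more than the documents support, in five ways.

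- **That the zero counts only spontaneous reports, or that there was no surveillance.** The documents say only that none were reported. Section 14.0 is confined to catheters ("This study includes the risk associated with the nasal placement of the manometry probe and pH/impedance catheter"), but it sits in a protocol that treats omeprazole as standard care. Section 17.0 opens with "Subjects are monitored throughout study procedures by a trained Registered nurse" and goes on to record review, weekly calls after discharge, a safety monitoring plan and quarterly DSMB meetings. Section 6.3 adds diaries and readmission tracking. What can be said is that the available text shows no adverse-event definition or collection form; the safety plan is referred to but not reproduced.
- **That the omeprazole doses reported at follow-up show treatment beyond 4 weeks.** They give a dose and not a duration, and revision 4 separately allowed increases.
- **That the Limitations section confirms continuation.** Its remark about reluctance to stop the drug sits under barriers to recruitment, so it does not clearly show this.
- **That feeding setbacks were missed adverse events.** In Table 3, row "Maintained PO", 16 of 17 conventional infants stayed on full oral feeds, so 1 did not. All 17 orally fed study infants did. Table 2 has 3 study infants on tube feeds only at Time 2, and Table 1 has 2 study infants gavage-fed at inception, so at least 3 − 2 = 1 moved from partial oral to tube feeding. These are prespecified feeding outcomes already shown by arm, and nothing in the documents requires counting them again as adverse events.
- **That an untreated group would be unsafe.** The trial does not show that either. It is uninformative in both directions.

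**Conclusion.** The concern holds as a fault of inference. The trial has no randomised infant assigned to go without acid suppression, so it cannot support a statement that withholding it is safe in infants with an acid reflux index of at least 3%. This rests only on the report's own description of the two arms and needs no assumption.

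The time-limited premise is unreconciled with revision 3 and section 6.1; the size of that discrepancy is unknown. The upper limits of 8.0%, 7.2% and 3.9% are conditional on complete ascertainment and apply only to omeprazole-assigned infants.

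No estimate, test or analysis population changes. What changes is what the trial may claim about safety. No view is taken here on dose, on duration of treatment, or on whether such infants should be treated.

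**What to change.** 1. In the Discussion, delete the inference that an untreated placebo group is safe. Say instead, for example: *All randomised infants were assigned omeprazole; the trial gives no information on the safety of withholding acid suppression.* The argument for a placebo trial on grounds of equipoise can stay.
2. Reconcile the time-limited and 4-week descriptions with revision 3 and protocol sections 6.1 and 8.0, and report per arm how many infants were still on omeprazole at Time 2.
3. In the adverse-events paragraph, keep the statement that none were reported. Add the denominator, the observation window and how events were ascertained. Give the limits of 8.0% (0/36), 7.2% (0/40) and 3.9% (0/76) with the condition that ascertainment was complete and the note that all apply to omeprazole-assigned infants.

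The cost is wording, three binomial limits and one count per arm. Section 6.1 says that refusals to stop are noted, and the report says that omeprazole compliance was confirmed from medical records and/or parents, so the count should be obtainable. The price is a less reassuring safety statement.

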## **CONCLUSION**

We addressed the current practice controversies in this clinical trial: 1) Screening and identifying acid-GERD objectively is possible in symptomatic infants prior to any pharmacotherapy. 2) Feeding strategy modification (fluid restriction, positional changes, prolonged feeding duration) has no role in decreasing reflux-type symptoms or in improving the primary outcome of achieving independent oral feeds and/or a six-point decrease in I-GERQ-R score. 3) No difference in the prevalence of chronic lung disease was noted between the groups. 4) I-GERQ-R scores decreased across time regardless of treatment group allocations that strongly

support maturational effect. However, we did not detect an effect on *a priori* short-term or long-term outcomes following randomized allocations. As restrictive feeding strategies do not make a difference, placebo-controlled clinical trials in a larger cohort of convalescing NICU infants with objectively determined newer GERD criteria must be addressed in future trials.

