## KEY POINTS

- Conservative feeding therapies are thought to modify GERD symptoms and its consequences. However, in this randomized controlled trial in convalescing neonatal ICU infants with GERD symptoms, when controlling for preterm or full-term birth and severity of esophageal acid reflux index, the effectiveness of acid suppression plus a feeding modification bundle (volume restriction, intra- and post- prandial body positions, and prolonged feeding periods) vs. acid suppression alone, administered over a 4-week period was not superior in improving symptom scores or feeding outcomes.
- Restrictive feeding strategies are of no impact in modifying GERD symptoms or clinically meaningful outcomes. Further studies are needed to define true GERD and to identify effective therapies in modifying pathophysiology and outcomes.
- The improvement in symptoms and feeding outcomes over time irrespective of feeding modifications may suggest a maturational effect. This study justifies the use of placebo controlled randomized clinical trial among NICU infants with objectively defined GERD.

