## STUDY OUTCOMES

### Primary and Secondary Clinical Outcomes

The clinically meaningful primary and secondary outcomes did not differ significantly between groups (**Table 2**). I-GERQ-R scores for study and conventional groups are shown (**Fig 2**). At inception: positive I-GERQ-R was 19/35 (54%) in the conventional group vs 24/37 (65%) in the study group,  $p=0.36$ . At Time-2: positive I-GERQ-R prevalence was 9/31 (29%) in the conventional group vs 13/34 (38%) in the study group,  $p=0.43$ . In the study group vs conventional group, respectively: a) primary outcome achieved in 33% (95% CI, 19% - 49%) vs 44% (95% CI, 28% - 62%) ( $p=0.28$ ), b) secondary outcomes: independent oral feeding in 65% (95% CI, 48% - 80%) vs 77% (95% CI, 60% - 90%),  $p=0.26$ ,  $\geq 6$ -point I-GERQ-R decrease in 38% (95% CI, 22% - 56%) vs 35% (95% CI, 19% - 55%),  $p=0.82$ , length of stay was 98 [81-132] days vs 108 [83-125] days,  $p=0.89$ , and oxygen requirement at discharge in 19% (95% CI, 8% - 35%) vs 26% (95% CI, 13% - 43%),  $p=0.49$ . There were no significant differences in growth metrics (all  $p>0.05$ ) or developmental scores at 2 years (all  $p>0.05$ ). Feeding outcomes or I-GERQ-R scores did not significantly differ between conventional vs study groups based on feeding method at inception (**Table 3**). Individual I-GERQ-R questions relating to vomiting, regurgitation, and crying (i.e. frequency of emesis, volume of emesis, symptoms with emesis, and crying more than usual in the

past week) had no differences ( $P>0.05$ ) within the group or between the groups across maturation for these individual symptoms, except for symptoms with emesis (never: rarely: sometimes: often: always, %) was 16:16:42:19:6 for conventional group at Time-1 vs 18:18:29:0:35 for study group at Time-1,  $p < 0.01$ .

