*Salient features of our study include:* 1) Allocations were unbiased and appropriately distributed between groups. 2) Among those presenting with GERD symptoms at inception, about 36% of infants had normal esophageal acid exposure, while 40% had abnormal acid exposure, and the rest in the indeterminate range. 3) The study bundle was not superior to acid suppression alone in improving primary outcomes or secondary outcomes. 4) Restricted feeding volume, body positions (intra- and post-prandial), oral or gavage feeding methods, supplemental oxygen, birth gestation and postnatal maturation did not influence the primary or secondary outcomes. 5) Reliability of compliance among those discharged was based on parental trust and available information. 6) There were no reported adverse events. No differences in long term developmental outcomes or economic burden measures, such as, LOHS, feeding methods and respiratory support at discharge were noted. 7) Symptom scores (I-GERQ-R) were significantly lower in both groups, suggesting that maturation may play a role in symptom modification, and not the bundled approaches. 8) Feeding outcomes improved in both groups.

*GMT Trial strengths and clinical implications are several:* 1) Random allocation, study design and protocol adherence were robust and rigorous. Although our strict inclusion criteria may have led to lower eligibility, our approach resulted in identifying infants carefully with true ARI as a marker of esophageal acid exposure. Objective determination of GERD based on ARI >7%

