to randomization would have resulted in all patients being treated based on subjective, non-specific symptoms alone. Owing to the strict inclusion and exclusion criteria of this RCT, those with indeterminate and abnormal ARI were treated with a PPI. In the future, a careful RCT that tests the utility of PPI treatment for confirmed acid-GERD by allocating patients to either limited PPI treatment or placebo is indicated to determine whether PPI treatment is needed. The effectiveness of our short-term use of PPI for 4 weeks to improve GERD-attributable symptoms should be tested in future trials. Effect of esophageal acid exposure and therapies on primary mechanistic outcomes of esophageal motility and symptom causation will be addressed in future reports. 5) In routine clinical practice, feeding volumes are modified and alterations in feeding positions are used to manage symptoms. Our study did not show any differences in the outcomes with feeding- and position modifications. Furthermore, volume restriction had no influence on the study outcomes. The improvement in symptoms and feeding outcomes over time irrespective of PPI or feeding modifications may suggest a maturational effect.

It is important to note that major mechanisms of GER, i.e. transient LES relaxation is the major reason for any reflux events- both acid or non-acid substrate. Our therapeutic target was acid reflux index in this study via PPI, feeding volumes, and positional changes. Given that acid GER can also have weakly or non-acid either before or after PPI therapy, and that there were no differences in outcomes between the two groups, we speculate that neither PPI, feeding volume, or positional changes modify the studied indices or symptoms. Maturation under optimal conditions of good nutrition along with placebo-controlled trials are needed to answer the importance of weakly acid or non-acid GER, which would require a multicenter trial with a large group of infants with appropriate physiologic diagnostic testing.

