**Table 2. Primary and Secondary Clinical Outcomes and Compliance Measures**

Primary Outcome (intent-to-treat analysis)	Overall (N = 76)	Conventional (N = 36)	Study (N = 40)	P-value
A priori clinical outcome Success, n (%)	29 (38)	16 (44)	13 (33)	0.28
Secondary Outcomes	Overall (N = 72)	Conventional (N = 35)	Study (N = 37)	P-value
I-GERQ-R decrease by 6 – n (%)	24/65 (37)	11/31 (35)	13/34 (38)	0.82
Feeding Outcome at Time 2 – n (%)				0.26
PO	51 (71)	27 (77)	24 (65)	
Transition (PO + Tube)	18 (25)	8 (23)	10 (27)	
Tube	3 (4)	0 (0)	3 (8)	
Length of hospital stay – days	108 [82 - 128]	108 [83 - 125]	98 [81 - 132]	0.89
Hospital stay Inception to Discharge – days	25 [11 - 45]	23 [3 - 39]	27 [16 - 47]	0.26
Weight Growth Velocity (GV) – g/day	27.1 (9.4)	26.5 (7.2)	27.6 (11.1)	0.64
Length GV – cm/day*	0.1 (0.1)	0.1 (0.1)	0.1 (0.1)	0.88
Head Circumference GV – cm/day*	0.1 [0.0 - 0.1]	0.1 [0.0 - 0.1]	0.1 [0.0 - 0.1]	0.87
Feeding Method at Discharge – n (%)				0.32
PO	54 (75)	29 (83)	25 (68)	
Transition (PO + Tube)	14 (19)	5 (14)	9 (24)	
Tube	4 (6)	1 (3)	3 (8)	
Oxygen Requirement at discharge – n (%)	16 (22)	9 (26)	7 (19)	0.49
Compliance to Feeding Methods				
Total Fluid Volume (TFV)				
TFV at Inception- #	N/A	150 [147, 152]	150 [149, 156]	0.8
TFV at Time 2- #	N/A	143 [134, 148]*	133 [126, 137]*	<0.001
# days TFV ≤ 140 / kg / day	N/A	10 [2, 26]	22 [11, 31]	0.005
TFV compliance (TFV <140/kg/d for >75% of time)	N/A	9 (26)	27 (73)	<0.001
Position				
Feeding Position, RSL, %	N/A	5 [1, 17]	78 [12, 94]	<0.001
Feeding in RSL >75% of the time, %	N/A	0 (0)	21 (57)	<0.001
Supine Position Post-Prandial, %	N/A	50 [40, 66]	87 [74, 96]	<0.001
Supine Position Post-prandial >75% of the time, %	N/A	7/34 (21)	27/36 (75)	<0.001
Feeding Duration				
% time feed duration >30 min, %	N/A	4 [0, 37]	15 [0, 69]	0.15
Feeding Duration at Inception, min	N/A	23 [17, 41]	30 [19, 34]	0.64
Feeding Duration at Time 2, min	N/A	23 [18, 28]	26 [20, 30]	0.15
Long-term Follow-up†				
Feeding Method at 6 months – n (%)				0.65
PO	36/50 (72)	21/27 (78)	15/23 (65)	
Transition (PO + Tube)	10/50 (20)	4/27 (15)	6/23 (26)	
Tube	4/50 (8)	2/27 (7)	2/23 (9)	
Feeding Method at 1 year – n (%)				0.11
PO	37/44 (84)	20/22 (91)	17/22 (77)	
Transition (PO + Tube)	4/44 (9)	0/22 (0)	4/22 (18)	
Tube	3/44 (7)	2/22 (9)	1/22 (5)	
CCABSID-III				
Cognitive Score <80 – n (%)	9/44 (21)	5/23 (22)	4/21 (19)	1.00
Cognitive Score – #	95 [90 - 105]	100 [90 - 105]	90 [90 - 100]	0.11

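### The Conclusion and Key Points state absolute nulls, partly for single components, that a two-arm superiority trial of one feeding bundle cannot support

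*Combined protocol and SAP*

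**What the plan says.** Three statements are absolute. Conclusion, item 2, reads "Feeding strategy modification (fluid restriction, positional changes, prolonged feeding duration) has no role in decreasing reflux-type symptoms" and extends the same denial to the primary outcome. The last sentence of the Conclusion takes it as settled that restrictive feeding makes no difference. Key Points, second bullet, reads "Restrictive feeding strategies are of no impact in modifying GERD symptoms or clinically meaningful outcomes".

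Two further statements assign the null to parts of the bundle. Discussion, salient features, item 4, reads "Restricted feeding volume, body positions (intra- and post-prandial), oral or gavage feeding methods, supplemental oxygen, birth gestation and postnatal maturation did not influence"; the sentence covers all endpoints. Discussion, strengths, item 5, reads "volume restriction had no influence on the study outcomes".

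The intervention itself was a package. Under Interventions, and in protocol sections 1.0 and 5.0, the study arm received right-lateral feeding, a supine position after feeds, a volume cap of 140 ml/kg/day and "feeding duration of at least 30 min utilizing pacing when orally fed". The other arm kept whatever feeding the providers recommended. Both arms received omeprazole. On delivery, the Results say: "Feeding duration of actual feeding was increased in the study group but not statistically different from the conventional group".

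Elsewhere the wording is more careful. The Abstract, the first Key Point and salient-features item 3 say that the bundle was not superior, and the Conclusion itself later says that no effect was detected.

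**The concern.** There are two separate problems. First, a non-significant result in a superiority trial is not evidence of no effect. What the trial excludes is read from the confidence interval for the difference. The report gives an interval for each arm, but none for the difference.

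Second, when four elements are assigned together, the contrast between arms estimates their joint effect as delivered. It says nothing about volume alone or position alone. One element could help while another hinders, or an element might hardly have been delivered. A statement that volume restriction had no influence needs a comparison that isolates volume, and none is reported.

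The Conclusion and Key Points are where clinicians and designers of later trials learn what has been ruled out. Taken literally, they would close the question for each element and for symptoms, which the data do not do.

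**Working it through.** **Inputs.** Table 2: primary success 13/40 study, 16/36 conventional; I-GERQ-R decrease of at least 6 points 13/34 and 11/31; compliance rows. Table 3: outcomes by feeding method at inception. Statistical Methods and protocol section 3.3: planned gain of 27 percentage points from about 40%, 80% power, one-sided 0.025.

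**1. Reported figures reproduced.** The uncorrected chi-square test gives p=0.284 for the primary outcome (reported 0.28) and p=0.818 for symptom response (reported 0.82). Exact binomial intervals for the primary are 18.6% to 49.1% and 27.9% to 61.9%, matching the printed 19–49% and 28–62%.

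**2. Intervals for the difference, study minus conventional.** Newcombe's method, with Wilson limits (l, u) for each arm:

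- lower = d − √[(p1 − l1)² + (u2 − p2)²]
- upper = d + √[(u1 − p1)² + (p2 − l2)²]

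*Symptom response.* p1 = 13/34 = 0.3824 (0.2390, 0.5496); p2 = 11/31 = 0.3548 (0.2112, 0.5305); d = +0.0275.

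- lower = 0.0275 − √(0.1434² + 0.1757²) = −0.199
- upper = 0.0275 + √(0.1672² + 0.1436²) = +0.248

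*Primary composite.* p1 = 13/40 = 0.3250 (0.2008, 0.4798); p2 = 16/36 = 0.4444 (0.2954, 0.6042); d = −0.1194.

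- lower = −0.1194 − √(0.1242² + 0.1598²) = −0.322
- upper = −0.1194 + √(0.1548² + 0.1490²) = +0.095

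**3. Sensitivity of these limits.**

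*Missing symptom scores.* Scores exist for 34 + 31 = 65 of 76 infants. Counting the other 11 as failures, as the plan does for the primary outcome, gives 13/40 against 11/36.

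*Success rule applied to Table 3.* Outcome Measures asks for either criterion in tube-fed infants and both in orally fed infants.

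- Tube-fed, either criterion: 14 conventional, 13 study. The row labels are displaced in the extracted text, but the counts confirm the assignment: 11 + 7 − 4 = 14 and 7 + 8 − 2 = 13.
- Orally fed, both criteria: 4 conventional, 5 study.
- Totals: 18 and 18, against 16 and 13 in Table 2. With all other randomised infants as failures, this is 18/40 against 18/36.

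| Outcome and counts | Difference (points) | 95% CI |
|---|---|---|
| Symptom response, 13/34 vs 11/31 | +2.8 | −19.9 to +24.8 |
| Symptom response, missing = failure, 13/40 vs 11/36 | +1.9 | −18.5 to +21.9 |
| Primary, Table 2, 13/40 vs 16/36 | −11.9 | −32.2 to +9.5 |
| Primary, rule applied to Table 3, 18/40 vs 18/36 | −5.0 | −26.1 to +16.7 |

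Both upper limits for the primary lie below +27. Neither lies at or below zero. For symptoms the upper limit is above 20 points either way.

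**4. Delivery of the components (Table 2, study vs conventional).**

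| Component | Study | Conventional | p |
|---|---|---|---|
| Volume criterion met | 73% | 26% | <0.001 |
| Right-side feeding >75% of the time | 57% | 0% | <0.001 |
| Supine after feeds >75% of the time | 75% | 21% | <0.001 |
| "Feeding Duration at Time 2, min", median [IQR] | 26 [20, 30] | 23 [18, 28] | 0.15 |
| % of time with feeds >30 min, median [IQR] | 15 [0, 69] | 4 [0, 37] | 0.15 |

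Three elements separated the arms in part. Feeding duration hardly did, and the study-arm median was below that arm's own 30-minute minimum.

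**5. Component comparisons.** Protocol section 3.3 planned models with feeding position or volume as covariates. The report shows no results from them. The number of randomised component contrasts is zero.

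**The case against.** The best defence is that the careful wording is already there. The Abstract, the first Key Point and salient-features item 3 say not superior, the Conclusion later says no effect was detected, and the limitations admit the recruitment shortfall. The failure of feeding duration to separate is reported openly. This lowers the risk of misreading, and it is why the point is minor. It leaves a report that states its main finding at two strengths, with the stronger form in the Key Points and Conclusion.

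A second defence also has force. The bracket in Conclusion item 2 is most naturally read as the contents of the bundle. A reader might infer that this sentence denies a role to each component, but the grammar does not require it. The component objection therefore rests on the two Discussion sentences, and item 2 is faulted only for the strength of its denial.

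Three other stronger readings should be resisted.

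- A reader might infer that not shown to be superior is all that the data allow. On the primary composite more can be said, because the planned 27-point gain is excluded on either set of counts.
- A reader might take about 10 points as a firm ceiling on the primary benefit. It depends on Table 2 counts that Table 3 does not reproduce; the alternative ceiling is near 17.
- A reader might want a disclaimer on left-lateral and prone positions, which the Introduction cites. No conclusion mentions them, and the Abstract and Interventions name the positions that were used. Listing untested postures is a matter of preference.

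**Conclusion.** Wrong as written, and minor. The statements of no role, no impact and no difference go beyond a two-arm superiority result, even for the whole bundle. For symptoms, a benefit of 20 points or more is not excluded (+2.8 points, 95% CI about −20 to +25). For the primary composite the planned +27 is excluded, but smaller benefits are not (upper limit +9.5 or +16.7, depending on the table). The separate claims about volume and positions have no reported comparison behind them, and prolonged feeding was hardly tested.

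None of this suggests that the bundle works: the primary estimate leans against it. The conclusion rests on Newcombe intervals, on the published counts, and on treating infants without a determinable success as failures in the Table 3 recount. The documents do not explain why Tables 2 and 3 differ, and the verdict is the same on either.

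**What to change.** - **Conclusion, item 2.** Replace with: *The feeding bundle (right-lateral feeding, supine post-prandial position, volume restriction, prolonged feeding) added to PPI was not shown to be superior to PPI with provider-directed feeding for symptoms or the primary outcome; the data exclude the planned 27-point benefit on the primary outcome but not a smaller one.*
- **Conclusion, last sentence, and Key Points, second bullet.** Use the same not-superior form.
- **Discussion, strengths, item 5.** Delete the volume sentence or restate it for the bundle.
- **Discussion, salient features, item 4.** Remove feeding volume and body positions as separate claims. Keep feeding method, oxygen, birth gestation and maturation only if an analysis supports them, since they are not parts of the bundle.
- **Limitations.** Add: *Bundle components were not tested separately, and feeding duration did not differ significantly between arms, so no conclusion is drawn about individual components.*

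The cost is wording in five places and one added sentence. The conclusion becomes narrower. No data collection, estimate or test changes, and no statement on other positions is needed.
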